4. POSSIBLE BENEFITS

No direct benefit to subjects is expected, although there may be some relief from IBS symptoms. However, this will help understand the pathophysiology of IBS-D and investigate the effect of low FODMAP diet on various physiologic parameters and even identify the predictors for response to this dietary intervention.

5. POSSIBLE RISKS AND ANALYSIS OF RISK/BENEFIT RATIO

The possible risks for the study include flexible endoscopy related complications such as bleeding or perforation. These are very unlikely to occur as we will be examining and taking biopsies from the last 20 cm of colon (and not performing polypectomies). These complications are very rare and unlikely to happen.

Blood Drawing

The risks and discomforts of blood drawing from a vein include the possibility of pain or bruising at the site of the blood draw; occasional feeling of lightheadedness; and rarely, infection at the site of the blood draw.

The benefit of this study is to help us understand how low FODMAP diet impacts the various gut functions- permeability, immune activation and microbiome. This will help us identify the patients who might benefit from this dietary intervention (as the diet is cumbersome to follow). Will also shed light on how diet interacts with gut physiology.

6. RECRUITMENT AND CONSENT PROCEDURES

Recruitment

Patients will be identified in the following ways:

- Clinical practice at Michigan Medicine
- GI referrals
- Review of medical records and appointment logs
- Advertisements
- UMHealthResearch.org
- Data Direct screens
- EMERSE screens

Potential study participants (obtained from the means listed above) will be approached or contacted by phone or email. A brief screening will be initiated to assess subject's eligibility before scheduling the office visit. Patients identified through clinical screening will be called using a phone script. Patients identified through a data direct / EMERSE screen will be re-screened and called by study staff to judge their eligibility and interest. Patients will be contacted three times before study team will cease contact.

Consent

During the Baseline Visit, a member of the study team will fully explain the purpose of the study to the patient and all questions and concerns regarding the study will be addressed as well (informed consent process). This will take place in a private area.

Subject Protection

None of the subjects in this study will be vulnerable to coercion or undue influence

7. STUDY LOCATION and DATA SECURITY

Privacy

All data will be kept in a password protected folder on the shared drive. All serum, urine and biopsy samples will be coded without patient identifiers and stored in restricted-access research areas at U of M. When the mucosal samples will be sent to a contract lab, they will not have any PHI labeled.

Physical Setting

All samples will be stored in freezers in restricted-access areas. All data generated from this study will also be stored in a password protected folder or in locked cabinets in locked offices.

8 Dissemination of Research Results

Patients will not be informed about the results of the study. Results might be presented/published.

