Colonic biopsies obtained pre- and post-dietary intervention will be used for this study. Formalin-fixed tissues will be embedded in paraffin and assembled into tissue microarrays before staining. After de-paraffinization, 5 µm sections will be rehydrated, and antigens will be unmasked by boiling in 0.01 M Tris/EDTA (pH 9.0). Slides will be stained with mouse anti-human ZO-1 monoclonal antibodies (catalog# 33-9100, Thermo Fisher Scientific), occludin polyclonal antibody (catalog# 71-1500, Thermo Fisher Scientific), rabbit polyclonal anti-claudin-1 (catalog# 51-9000, Thermo Fisher Scientific), rabbit polyclonal anti-claudin-3 (NBP1-48526, Novus Biologicals, Littleton, CO), rabbit polyclonal anti-claudin-8 (NBP1-59157, Novus Biologicals, Littleton, CO), rabbit polyclonal anti-claudin-15 (NBP2-13842, Novus Biologicals, Littleton, CO) primary antibodies. Primary antibodies will be detected using Alexa Fluor 594 or 488 conjugated secondary antibodies or highly purified secondary Fab'2 fragments (Jackson ImmunoResearch). Nuclei will be labeled with Hoechst 33342 (H3570, Thermo Fisher Scientific). Stained sections will be mounted in Prolong Diamond (Thermofisher Scientific). Tiled images will be collected on a DM4000 microscope equipped with Chroma filter sets (as above), a 20x HC PLAN APO NA 0.7 objective, CoolSNAP HQ2 grayscale CCD (for fluorescence) and Jenoptik ProgRes C10 Plus color CCD (for transmitted light, i.e., hematoxylin and eosin-stained sections) cameras, and a motorized xyz-stage (Ludl) controlled with custom MetaMorph 7 journals. Post-acquisition processing, including stitching of tiled images and quantitative analysis of signal intensity, will be performed using Metamorph 7 (Molecular Devices Sunnyvale, CA). The samples for this testing will be sent out coded without patient identifiers to the [name] Lab at U of M.

Serological tests for intestinal permeability

Following serological markers for intestinal permeability will be assessed: serum lipopolysaccharide (LPS) activity measured with the Limulus Amebocyte Lysate assay (LAL, Hycult Biotechnology, the Netherlands), and serum zonulin levels (Catalog number 30-ZONSHU-E01; ALPCO, Salem, NH). This will be performed at the [name] Lab at U of M.

Intra-epithelial and lamina propria mononuclear cell isolation

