Mononuclear cells will be obtained from colonic intra-epithelial and lamina propria fractions. Intra-epithelial (IELs) and lamina propria lymphocytes (LPs) will be isolated following incubation in dissociation buffer (HBSS Ca^{2+} and Mg^{2+} free containing 2% FBS, 5mM EDTA, 10 mM HEPES) and digestion buffer (HBSS with Ca^{2+} and Mg^{2+} , 10% FBS, 0.5 mg/ml DNase I and 0.5 mg/ml collagenase type IV), resuspension in 40% and layering on 80% Percoll Plus. IELs and LPs viability will be checked by Trypan blue exclusion.

Flow cytometry staining

Cell phenotype will be assessed by flow cytometry following cell incubation with fluorochrome-conjugated anti-human antibodies to: CD3, CD4, CD8, CD45RO, CD45RA, CD25, CD39, CD73, CD56 and CD117 (or c-KIT, marker of mast cell). Frequency of cells positive for FOXP3, RORC, T-bet and GATA-3 - transcription factors of Tregs, Th17, Th1 and Th2 lymphocytes will be assessed by intracellular staining following cell fixation and permeabilization with Cytofix/Cytoperm and incubation with fluorochrome-conjugated anti-human FOXP3, RORC, T-bet and GATA-3. Frequency of cytokine-producing cells will be determined after exposure to phorbol 12-myristate 13-acetate (PMA, 10ng/ml) and Ionomycin (500ng/ml) for 60 minutes and to Brefeldin A (20 μ g/ml) for additional 5 hours. Cells will be acquired on a BD LSRII and analyzed using BD FACSDiva software. 3-5 \times 10⁴ events will be acquired for each sample. Positively stained cell populations will be gated based on unstained, single stained and isotype stained controls. This will be performed at the [name] Lab at U of M.

Immunohistochemistry for immune cells

For immunohistochemistry, 5 μ m colon biopsy sections will be stained for human CD3, CD4, CD8, CD56, CD39, FOXP3, RORC, T-bet, GATA-3 and CD117 (or c-KIT). Endogenous peroxidase blocking with 3% H₂O₂ will be carried out. Sections will be incubated overnight at 4°C with primary antibodies to the above antigens and subsequently exposed to avidin/biotin complex with HRP (Vector Laboratories, Burlingame, CA). ImmPACT DAB (Vector Laboratories) was then applied and sections examined by light microscopy. This will be performed at the [name] Lab at U of M.

Mucosal and fecal microbiome

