Two colonic mucosal biopsies and stool samples obtained before and after the dietary intervention would be used for this analysis. Once obtained, each biopsy will be washed using Sterile PBS to remove non-adherent luminal/fecal material. The biopsy samples will be weighed, flash frozen in liquid nitrogen and stored at -80C for DNA extraction and microbiological analysis. DNA extraction will be done using a QIAamp DNA Mini Kit (Qiagen, Crawley, UK) per manufacturer's instructions. Bacterial community composition in isolate DNA samples will be characterized by amplification of the V1-V3 variable regions of the 16sRNA gene by polymerase chain reaction for both mucosal and fecal samples. 16S rRNA PCR products will be quantified, pooled and purified for the sequencing reaction. 454 GS FLX Titanium sequencing will be performed on a 454 Life Science Genome Sequencer FLX machine for both mucosal and fecal samples. Sequencing data generated will be processed by the Quantitative Insights into Microbial Ecology Pipeline (QIIME). Sequences will be screened for chimeras using the ChimeraSlayer algorithm, and all potential chimeras will be excluded from downstream analysis. Sequences less than 200 bp or greater than 1000 bp in length, those with average quality scores <20, incorrect primer sequences, or more than 1 ambiguous base will be excluded from downstream analysis. The quality filtered sequences will be assigned to operational taxonomic units (OTUs; sequences that share \geq 97% similarity) using a closed reference approach in QIIME with the UCLUST algorithm and the Greengenes reference database. According to the results of OTUs analysis, a diversity analysis including Simpson, Shannon, Chao 1, ACE and Good's Coverage will be carried out by QIIME. β diversity metrics, including (UniFrac weighed or unweighted) will also be calculated.

Stool samples will also be obtained from 30 healthy controls aged 18-65 years without any known gastrointestinal history and who do not report any abnormal bowel movements or abdominal pain. Stool samples from healthy controls will be utilized for analyzing fecal microbiome using the methodology described above. Their microbiome will be compared with microbiome of IBS-D patients pre and post LFD.

Clinical variables

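### No rule masks the laboratories to visit or runs a patient's pre- and post-diet samples together, so a directional reader or run shift could not be told apart from the diet effect

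*Combined protocol and SAP*

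**What the plan says.** Three sentences deal with coding, and all concern identity. Section 7, Privacy: "All serum, urine and biopsy samples will be coded without patient identifiers", and for outside work, "When the mucosal samples will be sent to a contract lab, they will not have any PHI labeled". Section 3.A, immunofluorescence: "The samples for this testing will be sent out coded without patient identifiers". None mentions visit, and none covers stool.

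The laboratory methods in Section 3.A bear on this as follows:

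- **Immunohistochemistry:** "sections examined by light microscopy". No scoring rule or masked reader is given.
- **Flow cytometry:** "Positively stained cell populations will be gated based on unstained, single stained and isotype stained controls". Masking of the operator is not mentioned, and no storage step before cell isolation is described.
- **Immunofluorescence:** "Formalin-fixed tissues will be embedded in paraffin and assembled into tissue microarrays before staining". Signal intensity is then quantified by software. No rule puts a patient's two cores on one array.
- **Sequencing:** "16S rRNA PCR products will be quantified, pooled and purified for the sequencing reaction". Which samples share a run is not stated.

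On design, Section 3.A puts all 40 IBS-D and 20 IBS-C patients on the diet, with the second sigmoidoscopy 28 days (±5) after the first. Healthy controls give one stool sample and leave the study. Section 3.B compares pre with post by paired t-test or Wilcoxon signed-rank test. It has no batch term, bridging sample or run order.

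**The concern.** Pairing removes stable differences between patients. It does not remove anything that is aligned with visit. Two laboratory effects can be aligned in that way:

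- A reader or gating operator who knows the visit, and knows that Section 1 predicts less immune activation and better barrier function after the diet, may score accordingly.
- If pre samples tend to be run earlier than post samples, a change in staining, reagent or instrument between runs falls on one side of the comparison.

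A trial with a concurrent control arm could estimate such a shift and subtract it. Here no untreated patient is sampled twice, so the shift would be reported as a diet effect, or would hide one. The second aim, T-cell and mast-cell abundance, rests on the two most operator-dependent readouts. The permeability and microbiome aims depend partly on assays run in batches.

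**Working it through.** **Inputs.** From Section 3.B: two-sided alpha 5%, d=0.5, pre-post correlation r=0.7, n=20. From Section 3.A: 40 IBS-D patients and 20 IBS-C patients. Shift sizes and batch SDs are not in the documents. The values 0.1, 0.2 and 0.3 are assumptions, in units of the SD of one measurement.

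**Step 1: the plan's own power.** The SD of a paired difference is √(2(1−r)) = √0.6 = 0.7746. The standardised difference is 0.5/0.7746 = 0.6455, and the noncentrality is 0.6455×√20 = 2.887. The exact noncentral t with 19 df gives 78.2% power, against the stated 80%. The plan's figure reproduces to within 2 points. With 40 pairs the noncentrality is 0.6455×√40 = 4.082 and power is 97.8%.

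**Step 2: a shift b in the same direction in every pair, no diet effect.** The noncentrality is (b/0.7746)×√n. The chance of p<0.05 is then:

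| b (SD) | Noncentrality, n=20 | False positives, n=20 | Noncentrality, n=40 | False positives, n=40 |
|---|---|---|---|---|
| 0.1 | 0.577 | 8.5% | 0.816 | 12.5% |
| 0.2 | 1.155 | 19.5% | 1.633 | 35.7% |
| 0.3 | 1.732 | 37.6% | 2.449 | 66.6% |

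More patients make this worse, because the test becomes more certain of a difference that the laboratory produced.

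**Step 3: the same shift working against a true d=0.5.** The net difference is 0.5−b. Power for b = 0.1, 0.2, 0.3 is 59.2%, 37.6%, 19.5% with 20 pairs and 89.0%, 66.6%, 35.7% with 40.

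**Step 4: batches that fall at random with respect to visit.** Take an independent batch effect with SD s on each sample, added to the unit variance. The variance of the difference becomes 0.6+2s², that is 0.62, 0.68 or 0.78. There is no bias, only lost power for d=0.5:

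| s (SD) | Standardised difference | Power, n=20 | Power, n=40 |
|---|---|---|---|
| 0 | 0.6455 | 78.2% | 97.8% |
| 0.1 | 0.5/√0.62 = 0.635 | 76.9% | 97.5% |
| 0.2 | 0.5/√0.68 = 0.606 | 73.0% | 96.2% |
| 0.3 | 0.5/√0.78 = 0.566 | 67.1% | 93.7% |

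Step 2 therefore describes a biased reader, or runs that separate pre from post. Step 4 describes batches unrelated to visit.

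**The case against.** The strongest reply has four parts.

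**Silence is not unmasking.** A reader might infer that the sample code shows the visit. The documents do not say so. The main coding sentence sits in a privacy section, where assay masking would not normally be described. This stands: the point is that masking is not stated, and that a shift may enter the change.

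**Batch effects need not be directional.** A reader might infer that the Step 2 rates apply to any batch problem. They do not. Recruitment through clinics, referrals and advertisements, with visits timed per patient, suggests staggered entry. One patient's post sample may then be processed near another's pre sample, which is closer to Step 4. This stands, and it makes the batch part of the point much milder. Still, the plan does not fix the run order, so runs that separate the visits are not ruled out.

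**Safeguards exist.** PCR is done in duplicate and normalised to GAPDH, immunofluorescence is quantified by software, flow gates are set against controls, and RNA and microbiome biopsies are kept at −80°C. These reduce noise and make paired runs possible. None of them masks visit or requires a pair to be run together.

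**Exposure is narrow.** Reader judgement enters mainly through immunohistochemistry and flow gating. It matters little for urine sugars by HPLC or the serum assays, although a run shift is not excluded there. This also stands.

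**Conclusion.** The point holds as an omission with a cheap remedy. The plan neither masks laboratories to visit nor pairs samples within runs, and its single-arm paired design cannot separate a directional laboratory shift from the diet. Immunohistochemistry and flow cytometry are most exposed. Software-quantified immunofluorescence, normalised PCR, serum assays and HPLC are less so.

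The size is conditional. Under an assumed same-direction shift of 0.1 to 0.3 SD with r=0.7, false-positive rates run from 8.5% to 37.6% with 20 pairs and from 12.5% to 66.6% with 40. Under batches unrelated to visit, with SD 0.1 to 0.3, the loss is 1.3 to 11.1 points of power with 20 pairs (78.2−76.9; 78.2−67.1) and 0.3 to 4.1 points with 40 (97.8−97.5; 97.8−93.7). The documents do not show which case applies, or that any shift exists. The false-positive rates should not be read as this trial's expected error.

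The change should be made before samples are run or read, because it cannot be fully recovered afterwards.

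**What to change.** Replace the coding rule in Section 7 with a random code that hides patient, visit and group from laboratory staff and readers until results are locked. Extend it to stool.

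In Section 3.A, require each patient's stored pre and post samples to be run together, in random order, on the same tissue microarray and staining run, PCR plate, serum plate and sequencing run.

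For flow cytometry on fresh cells, keep the control-based gating. Have an operator masked to visit apply one prespecified gating strategy, and record the run date so that drift can be checked. Identical fixed gates at both visits should not be imposed: with runs about 28 days apart, they could carry instrument or staining drift straight into the pre-post change.

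The cost is a code list and a wait for the second sample before stored assays are run. Pre samples will also be stored about four weeks longer than post samples, so storage time should be recorded. No extra patients, visits, procedures or readers are needed, and the sample-size calculation is unchanged.
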